### **9.2. Contamination and non-use:**

Hair samples were collected at all study visits. A random 10% subset of all participants at enrollment visit and 10% subset of samples from follow up study visits from the standard of care group will be analyzed for doxycycline drug concentrations to summarize instances of doxycycline detection at study enrollment (prior to dPEP initiation) or in the standard of care group. All hair samples collected in follow up study visits in the treatment group will be analyzed for instances of doxycycline non-detection, i.e., non-use (excluding participants with no sexual exposure reported in the last month). The percentage of participants with doxycycline detected in standard of care group will be compared with percentage of participants with doxycycline detected in dPEP arm over time, quarterly.

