**Adherence:** All participants will receive 1:1 adherence counselling for PrEP with individualized barrier identification and problem-solving assistance. Participants in the dPEP arm will receive 1:1 adherence counselling as well as reminders on their daily PrEP tablet bottle as a reminder to assess personal need for dPEP on that day. A number of measures will be used to determine adherence:

**Self-reported measures:** Sexual behavior and, for those assigned to the dPEP arm, pill-taking behavior, will be measured by timeline follow-back calendar at each follow-up visit to assess exposures and dPEP use. Because dPEP is an exposure-driven medication, adherence is dependent on use of dPEP following each exposure.

**Real-time behavioral measurement (optional):** Weekly SMS will be sent in English, *KiSwahili* or *DhoLuo* as part of a momentary ecological assessment of adherence and exposure. Exposure (i.e., condomless sex) will be referred to by a code word for added privacy: for example, "How many times did you dance [have sex without a condom] this week?" [If in the dPEP arm] "How many times did you take dPEP this week?" We have used real-time SMS data collection in multiple prior PrEP studies in Kenya; cell phones are very common in Kenya (outnumbering citizens). Encrypted transmission, password protection to open the surveys, and immediate deletion permit sensitive data to be collected safely. Studies of PrEP demonstrated that there was improved comfort with reporting sexual behavior via SMS, though objective adherence measures were far superior to self-report.

**Objective measures:** Hair drug levels will be measured to more objectively assess quantitative exposures to dPEP, for several analyses. Hair samples (50-100 strands) will be collected following consent to collection and confirmed eligibility for hair collection (occipital hair >0.5cm in length with absence of bleaching) from all participants at each visit (Months 0/3/6/9/12). Hair samples will be shipped to [name] UCSF Hair Analytical Laboratory (HAL).

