### **Pregnancy, breastfeeding, and HIV seroconversion**

#### *Management of dPEP with contraceptives and pregnancy:*

Contraception will be offered on-site but will not be required for study participation. The effectiveness of contraceptives or dPEP will not change with concomitant use. Women will be counseled on current Kenyan guidelines, which do not recommend use of doxycycline in pregnant women and participants

will stop dPEP should pregnancy occur. Women, who are not using LARC, will be screened for possible pregnancy at each quarterly visit using the WHO pregnancy checklist and if needed a urine pregnancy test will be conducted. Women will be counseled on current Kenyan guidelines, which do not recommend use of doxycycline in pregnant women and participants will stop dPEP should pregnancy occur; women can resume dPEP when no longer pregnant or breastfeeding. Pregnancies will be followed to completion. Any babies born to participants during the trial period will be passively followed for 1 year following their birth. Participants who deliver a baby during the trial will be asked to return for scheduled, quarterly study visits for a total of up to 12 months even though dPEP will be stopped if they are in the dPEP group. Additionally, they will be asked about the health of their baby at each study visit with continuation of questionnaire on health of their infant for first 12 months of infant's life. Breastfeeding will be an exclusion criterion for the trial, to limit exposure prior to demonstration of effectiveness; doxycycline is generally felt to be safe at standard doses in lactating women, although no formal declaration of safety exists for this population. Doxycycline is well-tolerated and recent data emphasize a strong safety profile when used by women, including in early pregnancy. Early data on safety of tetracycline found potential adverse effects when used in late pregnancy (specifically, bone and tooth effects), and cautions were extended to the entire tetracycline class, including doxycycline, despite lack of drug-specific data. Expert opinion is now calling for reconsideration of doxycycline use in pregnancy given significant differences between doxycycline and tetracycline and lack of evidence showing adverse events with doxycycline exposure in pregnant women.

*Management of PrEP with contraceptives and pregnancy:*

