## 9.0 CRITERIA FOR DISCONTINUATION

### Premature Study Treatment Discontinuation

- Requirement for prohibited concomitant medications or other contraindication to doxycycline
- Occurrence of an AE requiring discontinuation of doxycycline
- Request by participant to terminate study treatment
- Clinical reasons believed life threatening by the physician, even if not addressed in the toxicity section of the protocol
- Requirement for chronic tetracycline use (>14 days)
- Pregnancy
- Breastfeeding

Participants who stop dPEP should be continued on study, off dPEP with continued evaluations. The reason for doxycycline discontinuation should be recorded.

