### Descriptive:

EchoMobile SMS data: Past-week use of dPEP by reported sex acts among dPEP study arm participants in a table over all follow-up time, excluding periods where participant is on a documented study drug hold.

Timeline follow-back calendar: Past 2-week (day -14 to -3) participant-reported dPEP coverage among those with reported sex, by scheduled visit and over all follow-up time, excluding visits where participant is on a documented study drug hold.

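### SAP 9.2 has no drug-hold exclusion like that in SAP 8.5.1, so its hair-based non-use figure mixes instructed stopping of dPEP with non-use among women permitted to take it

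*SAP*

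**What the plan says.** **Hair measure.** SAP 9.2 (Contamination and non-use) says "All hair samples collected in follow up study visits in the treatment group will be analyzed for instances of doxycycline non-detection" and equates non-detection with non-use. It states one exclusion: "excluding participants with no sexual exposure reported in the last month". It says nothing about drug holds or discontinuations. The same section then compares the percentage with doxycycline detected between the standard of care and dPEP arms, quarter by quarter.

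**Self-report measures.** SAP 8.5.1 (Coverage of sex acts) summarises the SMS data "excluding periods where participant is on a documented study drug hold" and the timeline follow-back calendar "excluding visits where participant is on a documented study drug hold".

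**Who is off drug but still observed.** The protocol, under Management of dPEP with contraceptives and pregnancy, says participants "will stop dPEP should pregnancy occur; women can resume dPEP when no longer pregnant or breastfeeding". Protocol section 8.0 holds or permanently stops doxycycline for certain toxicities. Section 9.0 lists pregnancy and breastfeeding among the reasons to stop treatment and adds: "Participants who stop dPEP should be continued on study, off dPEP with continued evaluations". Hair is collected from all participants at Months 0, 3, 6, 9 and 12, subject to consent and hair eligibility.

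**Hair window.** SAP 2.2.4 and item 2 of SAP 8.5.2 place a 1 cm segment at roughly 5 weeks to 1 week before the visit. SAP 9.2 does not name a segment.

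**The concern.** The one exclusion in 9.2 makes sense if the aim is to measure non-use when use was called for: a woman with no exposure had no reason to take a dose. A woman told to stop had no reason either, yet she stays in the denominator and her negative hair counts as non-use. The protocol points the same way. Its adherence analysis in section 10.0 counts self-reported unprotected sex together with undetectable hair drug level as a nonadherence event.

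The samples concerned will exist. The sexual-exposure exclusion will not reliably remove women who become pregnant, and the protocol offers contraception without requiring it. A pregnancy stop can outlast the four-week hair window and affect several quarterly samples from one woman.

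What is at stake is how a secondary adherence figure is read. As written, the 9.2 percentage cannot tell a reader how much hair-negativity comes from women who could have taken dPEP and how much from women following an instruction to stop.

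**Working it through.** The documents give no hold rate, no expected non-detection rate and no expected non-use figure, so there is no planned number to reproduce. The check is a comparison of the rules, followed by an illustration.

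**1. The rules side by side**

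| Measure | Section | No-exposure rule | Drug-hold rule |
|---|---|---|---|
| Hair non-detection, dPEP arm | SAP 9.2 | Excludes women reporting no sex in the last month | None stated |
| SMS coverage | SAP 8.5.1 | Tabulated by reported sex acts | Hold periods excluded |
| Calendar coverage | SAP 8.5.1 | Restricted to those reporting sex | Hold visits excluded |

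The hold rule is present for both self-report measures and absent for hair.

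**2. Formula**

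- h = share of eligible dPEP-arm hair samples (sex reported) taken while off drug by instruction. Assumed 2% to 15%.
- q = probability that such a sample is hair-negative. Assumed 1.0, or 0.7 to allow for holds shorter than the hair window.
- u = non-detection among samples not on hold. Assumed 20%, with 50% as an alternative.

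Reported non-use = h × q + (1 − h) × u

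Shift relative to u = h × (q − u)

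The shift is positive whenever q exceeds u, and zero if the two are equal.

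**3. Results: reported non-use (shift in percentage points)**

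| h | q = 1, u = 20% | q = 0.7, u = 20% | q = 1, u = 50% | q = 0.7, u = 50% |
|---|---|---|---|---|
| 2% | 21.6% (+1.6) | 21.0% (+1.0) | 51.0% (+1.0) | 50.4% (+0.4) |
| 5% | 24.0% (+4.0) | 22.5% (+2.5) | 52.5% (+2.5) | 51.0% (+1.0) |
| 10% | 28.0% (+8.0) | 25.0% (+5.0) | 55.0% (+5.0) | 52.0% (+2.0) |
| 15% | 32.0% (+12.0) | 27.5% (+7.5) | 57.5% (+7.5) | 53.0% (+3.0) |

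Worked entry: h = 10%, q = 1, u = 20% gives 0.10 × 1 + 0.90 × 0.20 = 0.28.

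**4. Timing**

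The hair period ends about a week before the visit. A hold that began in the last week lies outside it, and a hold that ended in the last week may fill it. Hold status on the visit date is therefore the wrong flag for hair. What matters is status over the period the segment covers.

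**The case against.** The strongest reply is that 9.2 measures what it says it measures. A woman on hold is in fact not using the drug, and SAP 8.5.2 says hair will describe use against non-use rather than event-based adherence. Section 9.2 sits outside the adherence section and ends in a between-arm exposure contrast, where keeping everyone fits the intention-to-treat approach. All of that stands. A reader might infer that 9.2 simply overstates non-use, and the documents do not support this. What rises is the figure when it is read as non-use among women permitted to take dPEP. The section's own exposure exclusion and the protocol's nonadherence definition invite that reading.

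A reader might also infer that the hair and self-report measures cannot be compared, or that any gap between them will be taken for over-reporting. Neither follows. No section plans to set the 9.2 percentage against 8.5.1 coverage. The constructs differ anyway: any detection over about four weeks, against a dose within 72 hours on 80% of days with sex. The hair-to-SMS analysis in 8.5.2 uses a matched window and states no hold exclusion on either side. The denominators differ as written, but they can be aligned.

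Three further points on the other side also stand:

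- SAP 7.6 already tabulates CRF-documented time on drug, and SAP 8.1.3 lists discontinuation reasons. A reader will see how much off-drug time there was, though not split by hair result.
- The SAP does not say whether a documented hold in 8.5.1 covers pregnancy-related or permanent stops, so the exact extent of the asymmetry is uncertain.
- Short holds may leave drug detectable. Dropping every sample whose window merely touches a hold would remove women who were on drug for most of it.

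**Conclusion.** The concern holds in limited form. SAP 9.2 and SAP 8.5.1 treat drug holds differently, without explanation, and the 9.2 percentage mixes instructed stopping with non-use among women permitted to take dPEP.

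The direction is upward provided women on hold are more often hair-negative than the others. The size cannot be determined from the documents. At 20% non-detection off hold, the illustration runs from about +1 to +12 points for hold shares of 2 to 15%. At 50% it runs from +0.4 to +7.5 points. Every value of h, q and u is an assumption.

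A reader could obtain a more dramatic result, with the figure more than doubling from 10% to 23.5% (0.15 + 0.85 × 0.10). That needs the highest assumed hold share, low non-detection off hold and every hold sample negative, all at once. The documents support none of these values.

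This is a secondary descriptive figure. The primary efficacy test in SAP 7.5.1 is not affected.

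**What to change.** In SAP 9.2:

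- Keep the all-samples detection figure for the between-arm exposure contrast.
- Beside it, report dPEP-arm non-detection excluding samples for which the participant was on a documented hold or discontinuation for all or most of the period covered by the segment analysed. On the timing in SAP 8.5.2 that is 5 weeks to 1 week before the visit. Name the segment and state the overlap threshold.
- Use the CRF discontinuation dates already needed for SAP 7.5.3 and 7.6.

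In SAP 8.5.1 and 9.2 together:

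- Give a documented study drug hold one definition. Say whether it includes pregnancy, breastfeeding and permanent stops. Say also how it treats stops at the participant's own request, which are documented but not instructed. The protocol requires the reason for stopping to be recorded, so these can be separated.

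The cost is a few sentences and one merge of hair results with CRF dates. The SAP's introduction allows revision until database lock. The downside is a smaller denominator for the second figure, so the number of samples removed should be shown with it.

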#### *Hair testing:*

Hair samples from all participants will be collected. A subset will be shipped from University of Washington to [name] University of California San Francisco Hair Analytical Laboratory (HAL), which uniquely is able to do the required testing. Samples from three groups of participants will be analyzed: 1) 50 participants in the dPEP arm for dPEP and PrEP drug levels at each follow-up visit (Months 3/6/9/12), 2) any dPEP arm participant with incident STI, and 3) 10% all-comers (n=50) at enrollment (Month 0) and 5% of control arm at follow up visits (Months 3/6/9/12). Samples will be analyzed using liquid chromatography-tandem mass spectrometry (LC-MS/MS) testing for doxycycline hair level exposure over time (by hair segments representing weekly exposures) and hair levels of TVF

and FTC are a long-term metric of exposure to PrEP. Testing of additional samples may be done if the results of this pre-defined sample warrant.

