Adherence: We will explore the self-reported measures and SMS data, defining adherence as the percentage of times that dPEP was taken following an episode of condomless intercourse. Stored vaginal swabs for Y chromosome testing can be available for later validation, as noted in Aim 1 above. For hair, we plan three analyses, focused on 1) describing overall adherence in the population, 2) understanding the relationship between adherence and STI protection, and 3) exploring for cross-over (contamination between arms) that could occur since doxycycline is available in the community. We will complete a descriptive analysis of nonadherence events (defined as self-report of unprotected sex in last 3 months corresponding with elevated pill count or undetectable hair drug level), both for dPEP (dPEP arm only) and for PrEP, with log binomial regression with GEE to account for repeat measures of adherence over time. Adjusted analyses will control for potential confounders as in Aim 1.

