### **2.2.4. Adherence**

Adherence is only assessed in the dPEP arm

- Weekly SMS questions
  - Weekly questions collected in participants who opted in to SMS.
  - Number of days in the last 7 days when dPEP was taken
  - Number of days in the last 7 days when participants had sex or “danced”).
- Hair samples
  - Collected quarterly
    - Quantitative amount of doxycycline in 1cm segments from cut end to tip which corresponds with a 4-week period of dPEP use (starting 1 week ago).
- Self-report of coverage of sexual contacts in the prior 14 days to 3 days in the dPEP arm:
  - Quarterly (timeline follow-back) adherence questionnaire.

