#### Secondary analyses

2. Describe the relationship between quantitative tertials of doxycycline hair drug levels (low, medium, and high) and the number of dPEP doses reported in SMS in the 4-week time period of hair sample (5 weeks prior to study visit until 1 week prior to study visit) by generating a scatterplot and reporting the mean number of doses reported per quantitative category.
3. The mean hair drug concentration among hair samples collected at study visits when an incident STI (CT, NG, or TP, combined and per infection) was detected will be described and compared to study visits when no incident STI was detected among treatment group.

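### SAP 9.2 judges hair-based non-use over the last month, but the hair represents weeks 5 to 1 before the visit, so some correct users with only very recent exposure are counted as non-users

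*SAP*

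**What the plan says.** For follow-up hair from the dPEP arm, SAP 9.2 (Contamination and non-use) specifies that every sample is "analyzed for instances of doxycycline non-detection, i.e., non-use (excluding participants with no sexual exposure reported in the last month". The exposure period is therefore the month ending at the visit.

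The SAP describes the period that hair records in two places, and they agree. Section 2.2.4 speaks of "1cm segments from cut end to tip which corresponds with a 4-week period of dPEP use (starting 1 week ago". Section 8.5.2, under Secondary analyses, matches SMS-reported doses to the "4-week time period of hair sample (5 weeks prior to study visit until 1 week prior to study visit".

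The protocol has its own rule. In section 10.0 (Statistical power and analysis, Adherence paragraph) a nonadherence event is "self-report of unprotected sex in last 3 months corresponding with elevated pill count or undetectable hair drug level". Its Hair testing section describes the assay as done over time, "by hair segments representing weekly exposures", and sets no 5-to-1-week limit. Hair is eligible for collection if it is "occipital hair >0.5cm in length with absence of bleaching".

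Both documents make a dose due only after condomless sex, up to 72 hours later (Protocol 2.0, SAP 3.1).

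**The concern.** dPEP is event-driven. Without a qualifying exposure no dose is due, and negative hair is then what a fully adherent woman should show. Negative hair indicates non-use only if a dose fell due in the weeks that the hair records. SAP 9.2 tests for exposure over a different set of days, so it can retain women whose hair could not yet show their doses and drop women whose hair could.

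The wording adds a second problem. SAP 9.2 refers to sexual exposure and does not limit it to condomless sex. The protocol uses exposure to mean condomless sex in its SMS section. Unless the SAP intends the same, a woman who always used condoms, and so owed no dose, would also be counted as a non-user.

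Adherence is a stated objective in both documents, and hair is the one item that the protocol lists under objective measures. The window error can only turn correct users into non-users, so it overstates non-use in the women whom 9.2 retains.

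**Working it through.** **Hair window.** SAP 8.5.2: 5 − 1 = 4 weeks, or day −35 to day −7, which is 28 days. This agrees with SAP 2.2.4 (1 cm = 4 weeks, starting 1 week ago).

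**Overlap with the SAP 9.2 recall month.** The last 7 days of a 28- to 30-day month lie outside the hair window: 7/30 = 23% to 7/28 = 25% of the recall period. At the other end, 35 − 30 = 5 days (35 − 28 = 7 for a 28-day month) are in the hair but outside the recall.

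**Overlap with the protocol's 3 months, if one 4-week segment is assayed.** 90 − 28 = 62 or 91 − 28 = 63 days lie outside the hair window, 69% of the recall period.

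**Size of the mislabelling.** The documents give no rate of condomless sex, so the following is an illustration over an assumed range. Assume that every woman doses perfectly, every dose is detectable, and condomless acts follow a Poisson process at L per week. True non-use is then 0%.

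- SAP 9.2, 30-day month: no act in weeks 5 to 1 but at least one in the last week, given an act in the last 30 days: (1 − e^(−L)) · e^(−4L) / (1 − e^(−30L/7)).
- Protocol, one segment, 13-week recall: e^(−4L) · (1 − e^(−9L)) / (1 − e^(−13L)).
- Protocol, three 1 cm segments (weeks 13 to 1): e^(−12L) · (1 − e^(−L)) / (1 − e^(−13L)).
- SAP 9.2 with 0.5 cm of hair (0.5 × 4 = 2 weeks, so weeks 3 to 1), 28-day month: e^(−2L) · (1 − e^(−2L)) / (1 − e^(−4L)).

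Worked example at L = 0.25 for SAP 9.2: 0.2212 × 0.3679 / 0.6575 = 0.124.

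| Acts per week (assumed) | SAP 9.2 | Protocol, one segment | Protocol, three segments | SAP 9.2, 0.5 cm hair |
|---|---|---|---|---|
| 0.1 | 18% | 55% | 3.9% | 45% |
| 0.25 | 12% | 34% | 1.2% | 38% |
| 0.5 | 6% | 13% | 0.1% | 27% |
| 1 | 1.2% | 1.8% | about 0 | 12% |
| 2 | 0.03% | 0.03% | about 0 | 1.8% |

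Taking a 28-day month in the SAP column changes little: 19%, 13%, 6.2%, 1.2% and 0.03%.

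**After alignment.** If the exposure window equals the window of the assayed segment, no recall day lies outside it, and mislabelling from this source falls to 0 under the same assumptions. A small edge effect remains, because a dose taken up to 72 hours after sex can fall just past the window boundary.

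**The case against.** The strongest reply is that this is a 7-day offset in one descriptive tabulation, and that it bites only when sex is infrequent. SAP 9.2 can mislabel a correct user only if she had no dose at all in weeks 5 to 1. The 100 capsules per quarter are 50 doses, about 50/13 = 3.8 per week; that is a supply ceiling and not an expected rate, but it shows that the rates where the error matters are the low end. SAP 8.5.2 also says that hair assays are not standardized, that it will report use versus non-use and not event-based adherence, and that it assumes use is regular or absent. All of this stands as a limit on size. It does not make the rule correct: a woman can use dPEP regularly whenever a dose is due and still have had no exposure in the hair window. The SAP also aligns the windows itself when it compares hair with SMS doses.

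A reader might infer that the protocol definition is plainly the worse of the two. The documents do not establish that. The one-segment figures join the protocol's recall period to the SAP's 4-week window. The protocol speaks of weekly segments over time, the SAP of segments to the tip, and the protocol's wording can be read as requiring sex and hair result to match in time. What remains is that undetectable hair alone is enough to trigger the definition and that neither document says how many segments are assayed.

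A reader might also infer that this rate settles how a weak ITT result is read. No passage gives it that role. Calendar, SMS and pill-count data bear on adherence too, and the hair-based adherence-effectiveness model in SAP 8.5.2 does not use the 9.2 exclusion, so correcting 9.2 alone would not change it.

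**Conclusion.** The point holds in a limited form. By the SAP's own account of what hair records, the non-use rule in 9.2 uses the wrong exposure window. It misclassifies some correct users, those whose only exposure was in the last 7 days, and excludes some women with informative hair. It does not misclassify correct users in general.

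At assumed rates of 0.25, 0.5 and 1 act per week, about 12%, 6% and 1% of retained samples are affected, falling to near 0 at 2 per week. These figures rest on perfect dosing, full detectability, Poisson acts and hair that covers the whole 4 weeks; for hair near the 0.5 cm minimum they are much larger. The protocol's 34%, 13% and 2% at the same rates are conditional on a single 4-week segment.

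Only secondary and descriptive adherence results are affected. The primary ITT analysis is not. The rule should still be corrected, because it is a stated rule that gives a wrong classification and the change is cheap.

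**What to change.** - In SAP 9.2, classify non-detection as non-use only when condomless sex was reported in the same weeks as the hair segment assayed: weeks 5 to 1 for a 1 cm segment, and a correspondingly shorter window for shorter hair. A fixed day −35 to −7 window would still mislabel women with short hair.
- Name the exposure source. The protocol plans a 3-month timeline follow-back calendar, while SAP 8.5.1 describes only day −14 to day −3, which does not cover the hair window. Confirm which was collected and use the 3-month calendar if it exists. Otherwise use the SMS weeks for women who opted in, after checking that the SMS item meant condomless sex: the protocol defines the code word that way, but the SAP describes it simply as sex.
- Report samples without exposure data for the relevant weeks as unclassifiable, not as use or non-use.
- State how many segments are assayed per sample and how they combine into a detected/not-detected call.
- Bring the nonadherence definition in Protocol 10.0 into line with this rule.

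The cost is wording in both documents, which for the SAP can be settled before database lock, and fewer informative samples. If the 3-month calendar was not collected, the loss is larger, because SMS participation was optional.
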